#### **2.1.4.4 *Vital signs variables***

Vital signs include: heart rate (HR), systolic and diastolic blood pressure (SBP and DBP) in sitting position.

#### **2.1.4.5 *Electrocardiogram variables***

The ECG parameters were recorded automatically by the device at the Investigator site at Week -3/Week -2, Week 24, or early termination.

### **2.1.5 *Other endpoints***

The assessment endpoint listed below is defined using the same definitions and rules as for calculated LDL-C, when applicable (see [Section 2.1.3.1](#)).

- The absolute change in HbA1c (%) from baseline to Week 12 and Week 24. PCSA criteria for HbA1c will be used (see [Appendix A](#)).
- The proportion of patients with 2 consecutive results, spaced out by at least 21 days, of calculated LDL-C <25 mg/dL (<0.65 mmol/L) (respectively calculated LDL-C <15 mg/dL, ie, <0.39 mmol/L) during the treatment period and the time to the first calculated LDL-C <25 mg/dL (respectively, calculated LDL-C <15 mg/dL for these patients).

## 2.1.6 Anti-alirocumab antibodies variables

Anti-alirocumab antibodies are assessed at baseline (before the first IMP injection), at Week 4, Week 12, Week 24/or early termination and during follow-up (Week 32). Anti-drug antibody (ADA) measurements will be assigned to similar analysis windows as defined for efficacy endpoints ([Table 2](#)), with an additional analysis window for the ADA follow-up measurement performed at Week 32.

The following variables will be described:

- ADA response (Positive or Negative). For ADA positive
  - Titer levels;
  - Neutralizing status (Positive or Negative).
- Pre-existing positive ADA defined as patients with positive ADA response at baseline with less than 4-fold increase in titer in the post-baseline period;
- Treatment-emergent positive ADA response defined as 1) Patients with no ADA positive response at baseline but with any positive response in the post-baseline period (up to follow-up visit) or 2) Patients with a positive ADA response at baseline and at least a 4-fold increase in titer in the post-baseline period (up to follow-up visit). For treatment-emergent positive ADA, the following categories for ADA duration will be applied:
  - A persistent positive response is a treatment-emergent ADA positive response detected in at least 2 consecutive post-baseline samples separated by at least a 12-week period;
  - An indeterminate duration positive response is defined as ADA present only at the last sampling time point;
  - A transient positive response is defined as any treatment-emergent positive ADA response that is neither considered persistent nor indeterminate.

In addition, potential ADA samples to be collected after follow-up visit for patients with titer >240 at early end of treatment or follow-up visit will be listed.

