10.1.2.5 Visit 8/Week 24 (Day 169 ± 3): End of treatment visit

- Collect AEs
- Record concomitant medication
- Get body weight measurement
- Take vital signs including HR and BP
- Review patient's diet. Patient should be on a NECP-ATP III TLC diet or equivalent
- Perform 12-lead ECG
- Perform physical examination
- IVRS/IWRS contact to document the end of treatment
- Data collection on IMP administration and IMP compliance check by review of diary and treatment kit accountability.
- Urinalysis
- Urine pregnancy test (WOCBP only).

- Obtain fasting blood sample for:
 - Anti-alirocumab antibodies (to be performed prior to the IMP injection).
 - Lipids: measure and/or calculation of TC, LDL-C, HDL-C, TG, non-HDL-C, Apo B, Apo A-1, Apo B/Apo A-1 ratio and Lp(a)
 - Library samples
 - Hematology: CBC including RDW and reticulocyte count, hematocrit, Hb, red blood cell count, white blood cell count with differential blood count and platelet
 - Chemistry: glucose, sodium, potassium, chloride, bicarbonate, calcium, phosphorous, urea nitrogen, creatinine, uric acid, LDH, total protein, albumin and γ GT
 - Hepatitis C Antibody Test (with automatic confirmatory testing if positive)
 - HbA1c
 - Liver panel (ALT, AST, ALP, and total bilirubin)
 - CPK
 - Serum alirocumab concentration (PK)
- Reminders
 - An appointment will be given for the next study site visit.
 - Remind patient to be in fasting conditions (ie, overnight, at least 10-12 hours fast and refrain from smoking) for next study site visit, if needed. Also, alcohol consumption within 48 hours and intense physical exercise within 24 hours preceding the next study site visit are discouraged.
 - Sharp-container (containing all used auto-injectors) must be returned at site for destruction.

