10.3.4 Handling of patients after permanent treatment discontinuation

Patients who prematurely discontinue study treatment (regardless of the reason) should still continue the study and undergo all visits and procedures as described in [Section 1.2](#) with the exception of study treatment administration and its associated procedures. At the time of treatment discontinuation, the patient should have, as soon as possible, an unscheduled visit with assessments normally planned at end of treatment visit (this should take place within 5 days of treatment discontinuation, if possible) and then resume the original study schedule until end of study (ie, follow up visit). In particular, in case of early treatment discontinuation before week 24, all efforts should be done to perform the week 12 and week 24 visits.

If after treatment discontinuation, the patient refuses to continue the study, then if possible, the patient should undergo an unscheduled visit with assessments normally planned at the end of treatment visit (it should take place within 5 days of treatment discontinuation, if possible). The patient, at a minimum, should then be followed up for at least 10 weeks from last study treatment administration or up to recovery or stabilization of any AE to be followed-up as specified in this protocol, whichever comes last. A final end of study visit can take place with assessments as specified in the end of study visit (ie, follow up visit) at 10 weeks after the premature treatment discontinuation.

All definitive discontinuation of study treatment should be recorded by the Investigator in the appropriate screens of the e-CRF and in the patient's medical records when considered as confirmed. IVRS/IWRS should be notified when a patient prematurely discontinues study treatment.

For patients randomized and not treated, all efforts should be made to perform the Week 12 and Week 24 visits in order to collect the laboratory data and at the least, the lipid parameters.

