#### **2.4.7 Analyses of anti-alirocumab antibodies variables**

The following summaries will be performed on the ADA population, taking into account all samples regardless of timing relative to the injections:

- ADA results (negative or positive) by time point and by treatment group and also according to up-titration status;
- Neutralizing status (negative or positive) by time point for positive ADA and by treatment group and also according to up-titration status;
- ADA titers using descriptive statistics (median, minimum and maximum) for positive ADA by time point and by treatment group and also according to up-titration status;
- Number (%) of patients with pre-existing ADA and number (%) of patients with treatment-emergent ADA positive response by treatment group, overall and according to up-titration status;
- Number (%) of patients with persistent/transient/indeterminate treatment-emergent ADA positive response by treatment group, overall and according to up-titration status;

- Time to onset of treatment-emergent ADA positive response using descriptive statistics by treatment group, overall and according to up-titration status.

Correlations between ADA parameters (eg, titers, treatment-emergent ADA positive status, neutralizing status) and safety and/or efficacy endpoints will be also explored (eg, scatter plot).

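### An ADA response first seen at Week 24 and still present at Week 32 would be reported as transient, although it was never seen to end

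*SAP*

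**What the plan says.** SAP 2.1.6 schedules post-baseline ADA samples at Week 4, Week 12, Week 24 (or early termination) and Week 32. It counts a treatment-emergent response only up to the follow-up visit. It then assigns one of three duration classes:

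- Persistent: a treatment-emergent response "detected in at least 2 consecutive post-baseline samples separated by at least a 12-week period".
- Indeterminate: "An indeterminate duration positive response is defined as ADA present only at the last sampling time point".
- Transient: "A transient positive response is defined as any treatment-emergent positive ADA response that is neither considered persistent nor indeterminate".

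SAP 2.4.7 plans to report "Number (%) of patients with persistent/transient/indeterminate treatment-emergent ADA positive response by treatment group, overall and according to up-titration status", "taking into account all samples regardless of timing relative to the injections". Samples taken after the follow-up visit are listed, and no rule feeds them into the duration classes. The protocol gives no duration definition of its own: sections 9.3.1 and 11.4.4 cover antibody status and titers. Evaluating the development of these antibodies is a secondary objective (Protocol 5.2).

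**The concern.** The last two scheduled samples are only 8 weeks apart, so a response that starts at Week 24 cannot meet the 12-week rule when visits are on schedule. It is also shut out of the indeterminate class, because that class admits a response seen at the last sample and nowhere else. The residual class then labels it transient, which a reader will take to mean that the response went away.

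The ordering is perverse. A single positive at Week 32 is indeterminate because its end was not observed. Adding a second positive sample before it, which is more evidence of continuation, moves the patient to transient. At stake is the planned table by treatment group and up-titration status, where a reader would look for durability. For these patients the error runs one way: late responses not seen to end are counted as short-lived. The by-time-point ADA tables cannot correct this, since they do not show which patients were positive at both visits.

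**Working it through.** **Inputs.** Nominal days from Protocol 1.2: Week 4 = Day 29, Week 12 = Day 85, Week 24 = Day 169, Week 32 = Day 225. Visit windows from Protocol 10: ±3 days at Weeks 12 and 24, ±7 days at the follow-up visit. Persistence threshold: 12 × 7 = 84 days.

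**Nominal gaps.** 85 − 29 = 56; 169 − 85 = 84; 225 − 169 = 56 days.

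**Week 24 to Week 32 within the visit windows.** Shortest: (225 − 7) − (169 + 3) = 218 − 172 = 46 days. Longest: (225 + 7) − (169 − 3) = 232 − 166 = 66 days. Both are below 84.

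**All patterns.** A baseline-negative patient with four samples has 2⁴ − 1 = 15 possible positivity patterns. At nominal days:

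| Class | Current rule | With the change proposed below |
|---|---|---|
| Persistent | 4: W12+24; W4+12+24; W12+24+32; all four | 4: the same |
| Indeterminate | 1: W32 | 2: W32; W24+32 |
| Transient | 10 | 9 |

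The counts are the same whether the 12 weeks must separate two adjacent samples or may be the span of an unbroken positive run. Only W24+32 moves.

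**Early-stop route.** Protocol 10.3.4 covers patients who stop treatment and refuse to continue in the study. For the end-of-treatment assessments, "it should take place within 5 days of treatment discontinuation, if possible". The final visit can follow with the assessments specified "in the end of study visit (ie, follow up visit) at 10 weeks after the premature treatment discontinuation". Both visits include ADA (Protocol 10.1.2.5 and 10.1.3.1). If the first positive is at the end-of-treatment sample and the final sample is still positive, the gap is 70 − 5 = 65 to 70 − 0 = 70 days. If the ±7-day window applies to the final visit, it is 63 − 5 = 58 to 77 − 0 = 77 days. Both ranges are under 84, so the label is again transient.

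**Off-schedule samples.** SAP 2.5.4 Table 2 allows wider windows than the visit schedule. With a last injection on Day 155 (Week 22), the follow-up window is 155 + 70 ± 28, that is Days 197 to 253. The Week 24 window opens on Day 155. The largest possible gap is 253 − 155 = 98 days, so a badly off-schedule pair could count as persistent.

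**Week 12 to Week 24 within the visit windows.** Shortest: 166 − 88 = 78 days. Longest: 172 − 82 = 90 days. An on-protocol pair can therefore miss 84 days. The 4/1/10 and 4/2/9 counts hold at nominal days only.

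**The case against.** The literal logic is hard to dispute; the case against is about weight and scope.

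- **Low stakes.** Duration class is an SAP addition, and it feeds one descriptive table. Treatment-emergent incidence, titers, neutralizing status and time to onset are unaffected. This stands, and it limits the importance of the point.
- **Partial mitigation.** Time to onset will show late responses at group level. Patients with a follow-up titer at or above 240 are sampled further (Protocol 9.3.1.1), and the SAP lists later samples. This narrows the harm but does not change the label, because listed samples enter no duration class and responses with titers below 240 are not followed to resolution.
- **Transient is openly a residual class.** True, but the table will carry the word transient, and the SAP already recognises an unobserved end as a separate case.
- **The change is partial.** Of the eight patterns positive at Week 32, five are transient under the current rule (W24+32, W4+32, W12+32, W4+12+32, W4+24+32), and one of them moves. The other four contain a negative sample after first detection, so classing them is a judgement; W24+32 contains none.
- **The counts are nominal.** Correct. With a Week 12 to Week 24 gap of 78 to 83 days, W12+24+32 is persistent by run span but not by adjacent pair. On the adjacent-pair reading this adds another unbroken response labelled transient, which the same change would also handle.
- **The early-stop route is conditional.** It applies only to patients who refuse to continue, and both visits depend on feasibility. An early end-of-treatment sample on Days 127 to 154 falls in no Table 2 window, and one on Days 99 to 126 falls in the Week 16 window, which is not a scheduled ADA time point. However, SAP 2.1.6 names early termination as an ADA sampling point and SAP 2.4.7 takes in all samples. The route therefore stands if such samples are used for classification; the main case does not depend on it.

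**Conclusion.** The concern holds. For a baseline-negative patient with visits inside the protocol windows, the SAP wording labels an unbroken response running from Week 24 to the last scheduled sample as transient. On the nominal schedule this is one of 15 patterns. Patterns are not patients: the documents give no ADA incidence, so the number affected cannot be stated. The count does not cover baseline-positive patients who qualify through a 4-fold titer rise. The consequence is confined to the descriptive duration table in SAP 2.4.7; no test, type I error or efficacy estimate is touched. It should be corrected, because the table serves a stated secondary objective and the remedy is cheap.

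**What to change.** In SAP 2.1.6, define an indeterminate response as a treatment-emergent response that does not meet the persistent definition and is positive at every sample from its first detection through the last sampling time point. Leave persistent unchanged and keep transient as the residual class. An unbroken response still present at the last sample is then never reported as transient.

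Two details need a decision in the text. For baseline-positive patients who qualify by titer rise, the SAP should state which sample counts as first detection. Whether intermittent responses that are positive at the last sample also become indeterminate is the sponsor's choice, but it should be written down.

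The cost is SAP wording and derivation code, with no new data; the indeterminate class becomes slightly larger. As a separate minor point, the SAP listing of later samples uses a titer above 240, while Protocol 9.3.1.1 triggers extra sampling at 240 or above; the two should be reconciled.

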## 2.1.7 Pharmacokinetics variables

Concentrations of total alirocumab, total and free proprotein convertase subtilisin/kexin type 9 (PCSK9) concentrations in serum are assessed at baseline (Week 0), Week 4, Week 12, Week 16, Week 24, and during the post-treatment follow-up visit (Week 32). To collect information on the absorption phase, an optional PK sample can be collected 5 days ( $\pm 2$ ) after the Week 22 IMP injection.

Pharmacokinetic variable is the total alirocumab concentration at each time point. Depending on the timing of the sample versus the previous injection,  $C_{\text{trough}}$ ,  $C_{\text{trough,av}}$ ,  $C_{\text{max}}$  and  $C_{\text{Follow-Up}}$  will be defined as follows:

- $C_{\text{max}}$ : alirocumab concentration sample taken 5 days  $\pm 2$  days after previous injection;
- $C_{\text{trough}}$ : alirocumab concentration sample taken 14 days  $\pm 6$  days after previous injection (may be just prior the next injection):
  - $C_{\text{trough,av}}$ : Alirocumab average trough concentrations (" $C_{\text{trough,av}}$ ") will be calculated for each patient as the mean of " $C_{\text{troughs}}$ " considered at steady state. The occurrence of

steady state will be assessed graphically, by plotting “Ctrough” throughout the study visits over all patients.

- CFollow-up: alirocumab concentration sample taken more than 21 days after last injection and no more than 14 weeks after last injection.

Alirocumab concentration and total and free PCSK9 concentration will be described following time windows as defined in [Section 2.5.4, Table 2](#).

## 2.1.8 [REDACTED]

[REDACTED]

All critical or major deviations potentially impacting efficacy analyses, randomization, and drug-dispensing irregularities, and other major or critical deviations will be summarized in tables giving numbers and percentages of deviations by treatment group. Additionally, the analysis populations will be summarized in a table by number of patients on the randomized population.

- Randomized population;
- Efficacy population: intent-to-treat (ITT) population/modified intent-to-treat (mITT) population;
- Safety population;
- Pharmacokinetics population;
- Anti-alirocumab antibody population.
- Definitions of the study population are provided in [Section 2.3](#).

### **2.2.1 Randomization and drug dispensing irregularities**

Randomization and drug-dispensing irregularities occur whenever:

1. A randomization is not in accordance with the protocol-defined randomization method, such as a) a patient is randomized based on an incorrect stratum, b) a patient is randomized twice.

OR

2. A patient is dispensed an IMP kit not allocated by the protocol-defined randomization, such as a) a patient at any time in the study is dispensed a different treatment kit than as randomized (which may or may not contain the correct-as-randomized IMP), or b) a nonrandomized patient is treated with IMP reserved for randomized patients.

Randomization and drug-dispensing irregularities will be monitored throughout the study and reviewed on an ongoing basis.

All randomization and drug-dispensing irregularities will be documented in the clinical study report. These irregularities will be summarized among randomized patients (number and percentages). Nonrandomized, treated patients will be described separately.

Randomization and drug-dispensing irregularities to be prospectively identified include but are not limited to:

---

***Randomization and drug allocation irregularities***

---

*Kit dispensation without IRT transaction*

*Erroneous kit dispensation*

*Kit not available*

*Randomization by error*

*Patient randomized twice*

*Stratification error*

*A kit allocated at Day 1 or any unscheduled replacement before Week 12 is administered to the patient after the up-titration visit (Week 12)*

---

## **2.3 ANALYSIS POPULATIONS**

Patients treated without or before being randomized will not be considered randomized and will not be included in any analysis populations. The safety experience of patients treated and not randomized will be reported separately.

The randomized population includes any patient who has been allocated to a randomized treatment by IVRS/IWRS regardless of whether the treatment kit was used.

For any patient randomized more than once, only the data associated with the first randomization will be used in any analysis population. The safety experience associated with any later randomization will be assessed separately.

The safety experience of patients treated and not randomized will be reported separately, and these patients will not be in the safety population.

### **2.3.1 Efficacy populations**

The primary efficacy analysis population will be the ITT population.

#### **2.3.1.1 Intent-to-treat population**

The intent-to-treat population is the randomized patients who had an evaluable primary efficacy endpoint. The primary efficacy endpoint is evaluable when the following 2 conditions are met:

- Availability of a baseline calculated LDL-C value;
- Availability of at least 1 calculated LDL-C value within one of the analysis windows up to Week 24.

Patients in the ITT population will be analyzed according to the treatment group allocated by randomization (ie, as-randomized treatment group).

### **2.3.1.2 *Modified intent-to-treat population***

The modified intent-to-treat population is defined as all randomized patients who took at least 1 dose or part of a dose of the double-blind IMP injection and had an evaluable primary efficacy endpoint during the efficacy treatment period. The primary efficacy endpoint is evaluable when the following 2 conditions are met:

- Availability of a baseline calculated LDL-C value;
- Availability of at least 1 calculated LDL-C value during the efficacy treatment period within one of the analysis windows up to Week 24.

The efficacy treatment period is defined as the time period from the first double-blind IMP (capsule or injection, whichever comes first) up to the day of last injection +21 days or the day of last capsule intake date +3 days, whichever comes first.

Patients in the mITT population will be analyzed according to the treatment group allocated by randomization (ie, as-randomized treatment group).

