STATISTICAL CONSIDERATIONS	
Sample Size Determination
 
A total sample size of 96 patients (64 in alirocumab and 32 in ezetimibe arms) will have 95% power to detect a difference in mean percent change in LDL-C of 20% with a 0.05 two-sided significance level and assuming a common standard deviation (SD) of 25% and all these patients having an evaluable primary endpoint.
 
Nevertheless, to meet registration requirement and provide safety documentation in participating countries the final total sample size will be 600 with a randomization ratio 2:1 (alirocumab: 400, ezetimibe: 200).
 
Analysis Population
 
Randomized population includes any patients who have been allocated to a randomized treatment regardless of whether the treatment kit was used or not.
 
The primary efficacy analysis population will be the ITT population, defined as the randomized population who had an evaluable primary endpoint. The primary endpoint will be considered evaluable when both of the following conditions are met:
 
The baseline calculated LDL-C value is available.At least one calculated LDL-C value is available within one of analysis window up to Week 24. 
The mITT population is defined as all randomized patients who took at least one dose or part of dose of the double-blind investigational medicinal product (IMP) (injection or capsule) and had an evaluable primary efficacy endpoint during the efficacy treatment period. The primary efficacy endpoint will be considered evaluable when both of the following conditions are met:
 
The baseline calculated LDL-C value is availableAt least one calculated LDL-C value is available during the efficacy treatment period and within one of the analysis windows up to Week 24. 
The efficacy treatment period will be defined as:
 
The time period from the first double-blind IMP (injection or capsule, whichever comes first) up to 21 days after the last double-blinded IMP injection or the day of last capsule intake + 3 days, whichever comes first 
Patients in the ITT and mITT populations will be analyzed according to the treatment group allocated by randomization.
 
The safety population consists of the randomized population who actually received at least one dose or partial dose of IMP (injection or capsule). The

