11.3.1.2 Modified Intent-to-treat (mITT) population

The mITT population is defined as the all randomized patients who took at least 1 dose or part of a dose of study drug (injection or capsule) and have an evaluable primary efficacy endpoint during the efficacy treatment period. The primary efficacy endpoint is considered as evaluable when the following 2 conditions are met:

- Availability of a baseline calculated LDL-C value;
- Availability of at least 1 calculated LDL-C value within one of the analysis windows up to Week 24 and during the efficacy treatment period.

The efficacy treatment period is defined as the time period from the first double-blind IMP (injection or capsule, whichever comes first) up to the day of last injection + 21 days or the day of last capsule intake date +3 days, whichever comes first.

Patients in the mITT population will be analyzed according to the treatment group allocated by randomization.

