11.4.2.2 Analysis of secondary efficacy endpoint(s)

Method for controlling the overall type-I error rate when testing the key secondary efficacy endpoints is described in [Section 11.4.2.3](#).

For key secondary efficacy endpoints (defined in [Section 9.1.2.1](#)) and other secondary efficacy endpoints (described in [Section 9.1.2.2](#)), descriptive summaries and analyses will be performed in the ITT population or mITT population depending on the estimand used.

For descriptive summaries, percent change from baseline in calculated LDL-C, TC, HDL-C, TG, and non-HDL-C will be provided at each time point for each treatment group. All measurements, scheduled or unscheduled will be assigned to analysis windows defined in the SAP in order to provide an assessment for these time points. Laboratory assessments other than the ones provided by the central laboratory will be excluded. For TG, measurements on not-fasting patients will be excluded. The time profile of each parameter will be plotted by treatment group with the corresponding SE. Similar tables (with either percent change from baseline or absolute change from baseline for the ratio) and plots will be provided for other efficacy parameters: ApoB, ApoA-1, ApoB/ApoA-1 ratio, Lp(a). For TG and Lp(a), summary statistics will include Q1 and Q3, and medians (instead of means) by time point will be plotted.

Multiple types of measurements are planned to be analyzed during differing time points in the trial, specifically continuous measurements expected to have a normal distribution (example: percent change in calculated LDL-C), continuous measurements expected to have a non-normal distribution (example: TG), and binary measurements (example: proportion of patients reaching LDL-C <100 mg/dL).

Continuous endpoints anticipated to have a normal distribution

Continuous secondary variables defined in [Section 9.1.2](#) anticipated to have a normal distribution (ie, lipids other than TG and Lp[a]) will be analyzed using the same MMRM model as for the primary endpoint. Specifically, the model will contain fixed categorical effects of treatment group, randomization strata, planned time points to Week 24, strata-by-time point interaction and treatment-by-time point interaction, as well as, the continuous fixed covariates of corresponding baseline value and baseline value-by-time point interaction.

Continuous endpoints anticipated to have a non-normal distribution

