## **1.5 MODIFICATIONS TO THE STATISTICAL SECTION OF THE PROTOCOL**

There are no major changes to the protocol statistical section.

The first patient was screened on 27 July 2016(screen-failed). The first patient was randomized on 11 August 2016. There are no planned interim analyses.

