### **2.1.3.2 Secondary efficacy endpoint(s)**

#### **2.1.3.2.1 Key secondary efficacy endpoints**

The key secondary endpoints are:

- The percent change in calculated LDL-C from baseline to Week 24 in the mITT population, using all LDL-C values during the efficacy treatment period (on-treatment estimand);
- The percent change in calculated LDL-C from baseline to Week 12 (ITT estimand);
- The percent change in calculated LDL-C from baseline to Week 12 (on-treatment estimand);
- The percent change in Apo B from baseline to Week 24 (ITT estimand);
- The percent change in Apo B from baseline to Week 24 (on-treatment estimand);
- The percent change in non-HDL-C from baseline to Week 24 (ITT estimand);
- The percent change in non-HDL-C from baseline to Week 24 (on-treatment estimand);
- The percent change in TC from baseline to Week 24 (ITT estimand);
- The percent change in Apo B from baseline to Week 12 (ITT estimand);
- The percent change in non-HDL-C from baseline to Week 12 (ITT estimand);
- The percent change in TC from baseline to Week 12 (ITT estimand);
- The proportion of patients reaching calculated LDL-C <70 mg/dL (1.81 mmol/L) at Week 24 (ITT estimand);
- The proportion of patients reaching calculated LDL-C <70 mg/dL (1.81 mmol/L) at Week 24 (on-treatment estimand);
- The percent change in Lp(a) from baseline to Week 24 (ITT estimand);
- The percent change in HDL-C from baseline to Week 24 (ITT estimand);

- The percent change in fasting TG from baseline to Week 24 (ITT estimand);
- The percent change in Apo A-1 from baseline to Week 24 (ITT estimand);
- The percent change in Lp(a) from baseline to Week 12 (ITT estimand);
- The percent change in HDL-C from baseline to Week 12 (ITT estimand);
- The percent change in fasting TG from baseline to Week 12 (ITT estimand);
- The percent change in Apo A-1 from baseline to Week 12 (ITT estimand).

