#### ***2.4.4.2.4 Sensitivity analyses of key secondary endpoints***

In order to assess secondary endpoints during the efficacy treatment period, the same statistical approach as described above from [Section 2.4.4.2.1](#) to [Section 2.4.4.2.3](#) will be applied during the efficacy treatment period in the mITT population (see [Section 2.3.1.2](#)).

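### The mITT dosing condition is injection or capsule in the protocol but injection only in the SAP; the difference is unexplained, sits under five gated tests, and probably affects few or no patients

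*SAP*

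**What the plan says.** Protocol section 11.3.1.2 defines mITT by a patient who "took at least 1 dose or part of a dose of study drug (injection or capsule". The protocol synopsis has the same rule: "took at least one dose or part of dose of the double-blind investigational medicinal product (IMP) (injection or capsule". SAP 2.3.1.2 instead requires that the patient "took at least 1 dose or part of a dose of the double-blind IMP injection and had an evaluable primary efficacy endpoint", with no mention of the capsule.

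The remaining conditions agree. Both documents require a baseline calculated LDL-C and at least one later value inside an analysis window and inside the efficacy treatment period. Both start that period at the first capsule or injection. Both end it at last injection + 21 days or last capsule + 3 days, whichever is earlier.

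SAP 1.5 states: "There are no major changes to the protocol statistical section". SAP 1.6, on statistical modifications, is marked not applicable.

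The population matters through the on-treatment endpoints. Protocol 11.4.2.2 says that "analyses will be performed in the ITT population or mITT population depending on the estimand used", and SAP 2.4.4.2.4 says that the same methods "will be applied during the efficacy treatment period in the mITT population". The first key secondary endpoint in SAP 2.1.3.2.1 names the population outright: "The percent change in calculated LDL-C from baseline to Week 24 in the mITT population, using all LDL-C values during the efficacy treatment period".

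**The concern.** A gated endpoint should have one pre-specified population. Here, whether a capsule-only patient belongs to the first key secondary test depends on which document the programmer follows.

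The SAP is also out of step with itself. Its efficacy treatment period (2.3.1.2), baseline definition (2.1.3) and safety population (2.3.2) all count either product. Only the mITT dosing condition omits the capsule. That looks like a drafting slip, but the documents do not say whether it is one.

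The trial is double-dummy, so the omission does not mean the same thing in each arm. In the ezetimibe arm the injection is placebo and the capsule is active. Under the SAP wording, a control patient who took only the active drug is left out of an on-treatment analysis, while one who took only the dummy injection meets the dosing condition. In the alirocumab arm the same rule leaves out only patients who never received alirocumab.

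**Working it through.** **1. Which tests use mITT.** SAP 2.1.3.2.1 and protocol 9.1.2.1 carry the same ordered list of 21 key secondary endpoints. Five use the on-treatment estimand:

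| Position | Endpoint | ITT counterpart |
|---|---|---|
| 1 | LDL-C % change, Week 24 | primary endpoint |
| 3 | LDL-C % change, Week 12 | position 2 |
| 5 | Apo B % change, Week 24 | position 4 |
| 7 | non-HDL-C % change, Week 24 | position 6 |
| 13 | LDL-C below 70 mg/dL, Week 24 | position 12 |

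Position 3, for example, reads "The percent change in calculated LDL-C from baseline to Week 12 (on-treatment estimand"). Under protocol 11.4.2.3 and SAP 2.4.4.3 each test needs significance of those before it, so position 1 gates the other 20.

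**2. Who is classified differently.** A patient must meet all four conditions:

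- took at least one capsule;
- never took even part of an injection;
- has a calculated LDL-C value on study day 15 or later (SAP 2.5.4, Table 2: the Week 4 window opens on day 15);
- has that value no later than last capsule + 3 days.

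The last two together require capsules until at least day 15 − 3 = 12. Against that, protocol 8.1.2 and 10.1.2.1 place the first injection at the site under staff supervision, and 10.1.2.1 places the first capsule there too. A qualifying patient missed that supervised injection and every later one, yet kept taking capsules for about 12 days or more.

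**3. Possible size.** The documents give no count. I assume 0 to 12 such patients, the upper end being 2% of 600, and a difference of d = 50 points in LDL-C percent change from the rest of the arm. Protocol section 4 expects about a 50% reduction on alirocumab 75 mg, so 50 points is roughly the gap for an alirocumab-arm patient who took only placebo capsules. For a control patient taking active capsules it is generous. Removing a fraction f of an arm shifts its mean by f × d:

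| Assumed patients | Same share in both arms | All in alirocumab (400) | All in ezetimibe (200) |
|---|---|---|---|
| 0 | 0 | 0 | 0 |
| 3 | 0.5% × 50 = 0.25 | 0.75% × 50 = 0.375 | 1.5% × 50 = 0.75 |
| 12 | 2% × 50 = 1.0 | 3% × 50 = 1.5 | 6% × 50 = 3.0 |

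The planned LDL-C difference is 20 points. The documents give no planned difference for Apo B, non-HDL-C or the proportion below 70 mg/dL, so there is no equivalent yardstick for positions 5, 7 and 13.

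**4. The plan's own figure.** The only related figure is the sample size: 64 and 32 patients, difference 20, SD 25, two-sided 0.05. The noncentrality is 20 / (25 × √(1/32 + 1/64)) = 3.695 on 94 degrees of freedom, which gives 95.5% power against the stated 95%. It reproduces, but it does not depend on the mITT definition and says nothing for or against this point.

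**The case against.** The strongest reply is that the affected group may be empty. That stands. The four conditions are narrow, the first injection is supervised, and 600 patients are randomized where 96 give 95% power. Each of the five tests also has an ITT counterpart that does not use mITT.

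A reader might infer three stronger things that the documents do not support.

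- *That the five endpoints have materially different populations in the two documents.* Only the dosing wording is shown to differ. Nothing shows that any patient will be classified differently.
- *That SAP 1.5 is untrue.* It speaks of major changes, and a difference that may touch no one need not be major. The fair criticism is that the difference is unexplained.
- *That the asymmetry between arms proves the SAP rule wrong.* The protocol rule has its own version of the problem, since it admits alirocumab-arm patients who took only placebo capsules. Either rule is applied identically to both blinded arms. The sound argument is consistency with the protocol and within the SAP.

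It may also be said that the end of the efficacy treatment period is undefined for a never-injected patient. Largely it is not: with no injection date, only the capsule limit of the earlier-of-two rule remains. SAP 2.5.3 does not separate an unknown last injection date from an injection never given, so a clarifying note is reasonable but not essential.

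**Conclusion.** The point holds as a genuine but minor contradiction between current definitions. The protocol synopsis and section 11.3.1.2 require an injection or a capsule, SAP 2.3.1.2 requires an injection, and SAP 1.5 and 1.6 give no reason. The SAP wording could exclude an ezetimibe patient who took only the active drug from the tests at positions 1, 3, 5, 7 and 13.

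The expected effect is zero to a few patients. That is a judgement from the supervised first dose, not a documented count. On the assumptions above, three patients move an LDL-C arm mean by at most 0.75 point, and twelve placed entirely in the smaller arm move it by 3 points, against a planned 20. No test result is likely to change. The primary ITT analysis and the sample size are unaffected under either wording.

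**What to change.** Before database lock, take one of two routes:

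- amend the dosing condition in SAP 2.3.1.2 so that a full or partial dose of either double-blind product, injection or capsule, qualifies, as in protocol 11.3.1.2; or
- if injection-only is intended, declare it as a change in SAP 1.5 and give the reason.

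Optionally, under the first route, add that for a patient who was never injected the efficacy treatment period ends at last capsule + 3 days.

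The cost is a few words in the SAP and a matching check of the population flag in the programs. No data collection, sample size or power figure changes.
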